4.3.2 EXCLUSION CRITERIA

Subjects will be excluded if they meet any of the following criteria:

1. Dermal disorder including infection at anticipated treatment sites in either axilla.
2. Previous botulinum toxin treatment of the axilla in the past year.
3. Expected use of botulinum toxin for the treatment of any other disease during the study period.
4. Known allergy to starch powder, iodine, lidocaine, or epinephrine.
5. Secondary hyperhidrosis, for example, hyperhidrosis that is secondary to other underlying diseases including hyperthyroidism, lymphoma and malaria.
6. Previous surgical treatment of hyperhidrosis including sympathectomy, surgical debulking of the sweat glands, subcutaneous tissue curettage and ultrasonic surgery.
7. Unwillingness to wash off antiperspirants and abstain use 72 hours prior to treatments or assessments.
8. Subjects with a history of a bleeding disorder
9. Active implants (e.g., pacemakers or defibrillators), or metallic implants in the treatment areas.)
10. Use of cholinomimetics, anticholinergics, or any oral herbal medicine treatments for hyperhidrosis.
11. Inability to withhold use of antiperspirants or any other topical treatments for hyperhidrosis within 72 hours prior to study treatments and assessments.
12. Unwillingness for complete shaving or removal of underarm hair within 12 hours prior to study treatments and follow-up visits.
13. Women who are pregnant, lactating, possibly pregnant or planning a pregnancy during the study period.
14. Inability to understand the protocol or to give informed consent.
15. History of chronic drug or alcohol abuse.
16. History of chronic or frequently recurring episodic (recurrent episode in past 12 months) autoimmune diseases such as Multiple Sclerosis, Crohn's Disease, Psoriasis, Myasthenia Gravis, Lambert-Eaton Syndrome that has required immune suppressant therapy (such as biologic drug or corticosteroid treatment)..
17. Concurrent therapy that, in the investigator's opinion, would interfere with the evaluation of the safety or efficacy of the study device.
18. Subjects who anticipate the need for surgery or overnight hospitalization during the study.
19. Subjects who, in the investigator's opinion, have a history of poor cooperation, noncompliance with medical treatment, or unreliability.
20. Concurrent enrollment in any study involving the use of investigational devices or drugs.
21. Use of antiplatelet agents / Anticoagulants (Coumadin, Heparin, Plavix) in the past 6 weeks;
22. Psychiatric drugs that in the investigators opinion would impair the subject from understanding the protocol requirements.

After subjects have provided informed consent and met the inclusion/exclusion criteria, the study procedures described in the following section will be performed. Subjects can be enrolled in the study and treated according to this protocol on the same day.

4.4 SCREEN FAILURES

A screen failure subject is one from whom informed consent is obtained and is documented in writing (i.e., subject signs an Informed Consent Form), but who does not receive a study treatment because of failure to meet all of the eligibility criteria. Screen failure subjects will be included in the total number of subjects enrolled (i.e., all subjects consented), but not counted towards the total subjects treated.

4.5 SUBJECT RANDOMIZATION AND TREATMENT GROUP ASSIGNMENT

Subjects are not randomized in this study. They will all be treated using the same treatment approach (see Section 5.1 for Study Treatment details).

4.6 STUDY IMAGES

Ultrasound images will be obtained of each axilla using the Ulthera® System at baseline. All starch iodine tests will be captured with digital images. All images will be captured using a 2D digital imaging system.

5. TREATMENT OF SUBJECTS AND FOLLOW-UP

This study involves two treatments 30 days apart completed at the treatment visit #1 and treatment visit #2 after obtaining informed consent, screening for inclusion/exclusion, confirming the completion of a washout period of at least 2 weeks from use of aspirin, Ibuprofen, Naproxen or any other NSAID, and Vitamin E, if applicable, complying with protocol specified photography requirements, completing a pregnancy test, if applicable, and completing any study specific baseline assessments.

5.1 STUDY TREATMENT

5.1.1 TRANSDUCERS

One transducer will be used during this trial – a 7 MHz transducer with 3.0mm focal depth.

The location to be treated, the transducer, and the energy level will be recorded on the Treatment Parameter System Record.

5.1.2 PRE-TREATMENT MEDICATIONS

[figure not shown]
All study subjects will receive injections of 1% lidocaine with epinephrine to each axilla prior to each study treatment.

5.1.3 SUBJECT PREPARATION FOR TREATMENT

- a. The investigator, sub-investigator, or delegated clinician will first assess the subject's hyperhidrosis based on:
 - Starch iodine test
 - Amount of subcutaneous soft tissue in region to be treated and the area to be treated

The treatment map identifies the areas and pattern where the Ulthera® treatment is to be performed (**Figure 5.1.3-1**). Treatment schematic is for illustrative purposes only. Treatment records for all regions will be maintained in accordance with this protocol.

FIGURE 5.1.3-1 TARGET TREATMENT AREAS

5.1.4 TREATMENT

All study treatments will be performed by the investigator, sub-investigator, or delegated clinician (i.e., study treatment clinician as designated by the principal investigator.)

Ultrasound gel will be applied to the transducer, which will then be placed on the targeted skin surface, and an ultrasound image will be obtained. Each area of the proposed treatment will be imaged first with the ultrasound device to ensure appropriate coupling between the transducer and skin. During the treatment procedure, the study treatment clinician will place multiple Ultherapy® treatment lines close to each other (2 to 3mm) in the selected area, with each treatment line requiring about 3 seconds. Treatment lines can be a maximum length of 25mm and will produce a series of thermal coagulative zones.

Treatment lines to the area highlighted in (**Figure 5.1.3-1**) above will be administered in a 3 x 4 grid (minimum), resulting in at least 12 treatment squares, depending on the size of each subject's axilla. Two Ultherapy® treatments will be provided at a 3.0mm depth, 30 days apart. At each treatment, study subjects should receive a minimum of 720 treatment lines, +10% variance, to each axilla (minimum of 1440 total lines of treatment for both axillae) delivering 60 treatment lines per treatment square. **The treatment lines must be delivered in multiple passes, with no more than 10 lines delivered per treatment square with each pass, for a total of at least 6 passes per square.** When delivering passes of treatment, all 12 treatment squares should be treated with 10 lines in sequential order (square 1, square 2 and so on), then once complete with the first pass the sequence is followed again to deliver a second pass of 10 lines per square until all 6 passes of 10 lines per square are completed.

The purpose of specifying the number of lines per pass and number of total passes is to minimize the risk of adverse events (AE). In a prior clinical trial, it was observed that AE rates were lower when this high-density treatment was delivered as stated above. The subject will be monitored during the treatment.

5.1.5 ACUTE RESPONSES

For all exposures, acute responses (e.g., erythema or edema) will be observed by the study treatment clinician and photographically recorded within 30-60 minutes after exposure. If any Serious Adverse Events (SAE) are noted, an SAE Form should be completed. Short-term post-treatment adverse events will be assessed via phone contact with study subjects following each study treatment at 7±2 days post-treatment.

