
Treatment Outline:
	
 1. Screening/Baseline/Treatment Visit #1: 
 a. Obtain Informed Consent and medical history; b. Screen for general inclusion/exclusion criteria; c. Obtain axillary ultrasound images of each axilla; d. Perform pregnancy screening test, if applicable;

	
 e. Complete baseline evaluations: HDSS, gravimetric, and starch iodine test with digital images of the result; f. Administer local anesthetic to both axillas; g. Perform bilateral Ultherapy treatment; h. Assess Numeric Rating Scale for Pain; and i. Assess for adverse events. 
 2. Post-treatment #1 telephone contact: 
 a. Capture adverse events (7±2 days). 3. Treatment Visit #2, 30 ± 7 days post-treatment #1: 
 a. Complete HDSS, gravimetric, and starch iodine test with digital images of the result; b. Perform pregnancy screening test, if applicable; c. Administer local anesthetic to both axillas; d. Perform bilateral Ultherapy treatment; e. Assess Numeric Rating Scale for Pain; and f. Assess for adverse events. 4. Post-treatment #2 telephone contact: 
 a. Capture adverse events (7±2 days). 5. Follow-up Visits post-treatment #2 for efficacy evaluation: 
 a. 30 ± 7 days 
 i. Complete HDSS, gravimetric test, and starch iodine test with digital images of the result; and ii. Assess for adverse events. b. 90 ± 7 days 
 i. Complete HDSS, gravimetric test, and starch iodine test with digital images of the result; ii. Assess for adverse events; and iii. Perform pregnancy screening test, if applicable.

Primary Endpoint:
	
HDSS score reduction from a 3 or 4 at baseline to a 1 or 2 at 30 days post-treatment #2.

Secondary Endpoints:
	
 1. Reduction in spontaneous axillary sweat production assessed by a gravimetric method at 90 days post treatment #2, as measured by a 50% reduction or more compared to baseline. 2. HDSS score reduction from a 3 or 4 to a 1 or 2 at 90 days post treatment #2. 3. Starch iodine test to assess area of efficacy with digital images.

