1.6.5 HYPERHIDROSIS PILOT STUDY

A randomized, double-blind, controlled pilot study was conducted to evaluate the efficacy and safety of the Ulthera® System for the treatment of primary axillary hyperhidrosis. The objective of study was to evaluate the efficacy and safety of the Ulthera® System for treatment of primary axillary hyperhidrosis.

Twenty subjects meeting inclusion and exclusion criteria were enrolled. These criteria included a score of 3 or 4 on the Hyperhidrosis Disease Severity Scale (HDSS) as well as >50mg/5 min of sweat production in both axilla as measures by gravimetric method. Active-treated subjects (N=12) received two treatments 28 days apart consisting of 240 lines each, using both 4MHz-4.5mm and 7MHz-3.0mm transducers, for a total of 480 lines per axilla. No energy was delivered during a similar treatment for Sham-treated subjects (N=8). Both groups received pre-treatment injections of lidocaine plus epinephrine. Efficacy at 7, 14, 30, 37, 44, 60, 90, and 120 days was measured by Hyperhidrosis Disease Severity Scale, gravimetric sweat production, and starch iodine test. Patient satisfaction was assessed at 30, 60, and 90 days (trial days 60, 90 and 120) after second treatment. The primary endpoint was response at 60 days (30 days after second treatment), defined as HDSS score of 1 or 2. Adverse events were collected at all follow-up time points and spontaneous reports were also collected.

Subjects were an average age 34 (range 21-52), 30% were female, 30% Caucasian, 50% Hispanic/Latino, 15% African American, and 5% Asian. No subjects responded to sham treatment, either at the primary endpoint visit or at any other visit throughout the study.

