At 30 days after second treatment (day 60 of trial), the response rate, as measured by HDSS, in the active treatment group was 67%, a significant difference compared to 0% in the sham group ($p = 0.005$, two-sided Fisher's exact test (FET)). Response to active treatment peaked 7 days after the second treatment (83%) and was sustained for the remainder of the trial. Ninety days after the second treatment (day 120 of the trial), 67% of subjects were still in response. Gravimetric measurement of sweat production showed similar results. At all follow-up study visits, sweat production decreased from baseline by at least 50% in the active treatment group but not in the sham group. Regardless of study visit, percent change from baseline in gravimetric measurement was significantly greater in the active treatment group than in the sham group ($p < 0.0001$, rank-based repeated measures analysis of variance). In the active treatment group, the greatest change from baseline (73.1%) was at 90 days after the second treatment (day 120 of the trial). Starch iodine testing qualitatively supported a reduction in sweat production in the active-treated subjects compared to sham-treated subjects. All but one subject at 30 and 90 days after second treatment and two subjects at 60 days after second treatment in the active-treated group were satisfied or very satisfied. None of the sham-treated reported satisfaction at any time point after the second treatment. Treatment-related AEs reported in the active-treated group were bruising in 3 subjects (15%) with an average duration of 3.3 days (range 2-5 days), soreness or tenderness in subjects (83%) lasting an average of 12.9 days (range 4-31 days) during which only 2 subjects took a single dose of ibuprofen the day after treatment, numbness in 1 subject (8%) lasting 13 days, and paresthesia in 3 subjects (25%) lasting an average of 13.3 days (range 10-18 days). Treatment related AEs reported in the sham-treated group were soreness in 2 subjects (25%) lasting 1 day, and paresthesia in 1 subject (12.5%) lasting 1 day. Average pain scores for both transducers during both treatments for the sham-treated group were 0.8 (range 0-5) while pain scores averaged 1.8 (range 0-5 for the active-treated group suggesting that blinding was sufficient).

Pilot study results suggest the Ulthera® System may be efficacious and safe for the treatment of axillary hyperhidrosis.

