5.4 FOLLOW-UP

Subjects will be asked to return to the clinic for follow-up visits at 30 and 90 days post-treatment #2.

The following assessments will be completed at all follow-up visits: gravimetric assessment, starch iodine test, and HDSS. Digital images of the starch iodine test will be obtained. At the last follow-up visit, a pregnancy screening test will be completed, if applicable. Safety endpoints and adverse events will be monitored at all follow-up visits.

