7. EVALUATION OF ADVERSE EVENTS

7.1 DEFINITIONS

An adverse event is defined as any new medical problem, or exacerbation of an existing problem, experienced by a subject while enrolled in the study, whether or not it is considered device-related by the investigator. Reported events will be categorized as Expected Treatment Effects, defined as: any typical treatment side-effect of Ultherapy® of mild to moderate severity and lasting up to a typical maximum duration (See **Table 8.1.1** for typical maximum durations), or as Adverse Events based on severity, duration and relationship to the Ulthera® device or Ultherapy® procedure/technique. See **Figure 7.1.1**.

FIGURE 7.1.1. EVENT REPORTING

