8. RISK ANALYSIS

8.1 POTENTIAL RISKS

This treatment modality was designed to inherently minimize the risk to the subject. However, ultrasound exposure with subsequent heating of the soft tissue could involve the risks listed in **Table 8.1.1** below:

TABLE 8.1.1 EXPECTED TREATMENT EFFECTS

Expected Treatment Effects	Duration
Bruising/Ecchymosis	Up to 3 weeks
Edema/Swelling	Up to 2 weeks
Erythema/Redness	Up to 1 week
Acute Pain	Immediate/momentary (while energy is being delivered) - 2 hours
Induration	Up to 12 weeks
Pruritus	Up to 2 weeks
Welting/Raised Areas of Edema	Up to 4 weeks
Skin Burn, Scarring, Change in pigmentation	Up to 8 weeks
Tenderness/Soreness/Pain/Sensitivity to Touch	Up to 3 weeks
/Muscle Twitching/Tingling/Paresthesia/Numbness	Up to 5 weeks
Reduced Range of Motion	Up to 3 weeks
Skin Peeling	Up to 2 weeks

Additional potential risks include: nerve injury, arterial blood spasm, change in axilla odor, and reduction of underarm hair growth.

The risks from lidocaine with epinephrine may include pain and discomfort from the injections, infection at the anesthetic site, lightheadedness, nervousness, mood change, tinnitus, blurred vision, vomiting, sensations of heat, cold or numbness, tremors, seizures, or unconsciousness. Additional uncommon side effects may include bradycardia, hypotension and cardiac arrest. Allergic reactions may appear as skin rashes, swelling or anaphylaxis.

Risk associated with a starch iodine test may include an allergic reaction to iodine solution or starch powder. No risks are anticipated from completion of a gravimetric sweat test or ultrasound imaging.

These risks will be minimized or reduced by monitoring the subject during the treatment and observing the skin's response to receiving the treatment. If the treatment is not tolerated, the investigator must stop administering treatment for the subject's safety, and the subject will be followed for adverse events for 90 days.

Previous clinical studies with the Ulthera® System have shown that the sensory response was tolerable from the subject's and investigator's perspectives. The discomfort was transient and no subject had any residual pain beyond 30 minutes.

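### All six 2-week and 3-week limits that help separate an Expected Treatment Effect from an Adverse Event fall between the day 5-9 call and the day 23-37 visit, so effects that end in that gap are classified from recall

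*Combined protocol and SAP*

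**What the plan says.** Section 7.1 defines an Expected Treatment Effect as "any typical treatment side-effect of Ultherapy® of mild to moderate severity and lasting up to a typical maximum duration", and refers to Table 8.1.1 for the durations. Other events are Adverse Events, judged on severity, duration and relationship to the device or procedure. Section 6.2 plans one safety presentation: the number of subjects reporting each adverse event and each device-related adverse event. It mentions no summary of Expected Treatment Effects.

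The contacts after a treatment are as follows.

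- Acute responses are observed and "photographically recorded within 30-60 minutes after exposure" (section 5.1.5).
- One telephone contact follows: "Short-term post-treatment adverse events will be assessed via phone contact with study subjects following each study treatment at 7±2 days post-treatment" (section 5.1.5).
- After the first treatment the next contact is "Treatment Visit #2, 30 ± 7 days post-treatment #1" (synopsis, Treatment Outline).
- After the second: "Subjects will be asked to return to the clinic for follow-up visits at 30 and 90 days post-treatment #2" (section 5.4). Table 3.1-1 gives each of these visits a window of ±7 days.

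AE forms are completed at the calls and the visits (Table 3.1-1). At each later visit the subject is asked about adverse events and the treated area is examined (section 5.2). The text provided mentions no diary and no other scheduled contact.

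**The concern.** For a typical side effect of mild or moderate severity, duration decides whether it enters the adverse event table. If the end of the effect is not observed, the site must ask the subject on which day it stopped, some days or weeks afterwards. An effect wrongly remembered as short drops out of the only planned safety table, and one wrongly remembered as long is added to it.

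This matters most for "Tenderness/Soreness/Pain/Sensitivity to Touch", which has a 3-week limit. In the pilot described in section 1.6.5, soreness or tenderness occurred in 83% of active subjects and lasted 4 to 31 days, so the limit cuts through the observed range. Section 5.1.4 also says the multi-pass delivery is meant to reduce adverse event risk, which makes the adverse event counts an important result of this study.

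**Working it through.** **Contact windows, in days after a treatment.** Call: 7±2 = day 5 to 9. Next visit: 30±7 = day 23 to 37. Last visit, after treatment #2 only: 90±7 = day 83 to 97. The interval between call and visit is 23 − 9 = 14 days at its shortest, 30 − 7 = 23 days nominally and 37 − 5 = 32 days at its longest.

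**The 12 limits in Table 8.1.1 against these windows.**

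| Limit | Effects | Position |
|---|---|---|
| 2 hours | acute pain | between the acute check and the call |
| 7 days | erythema | within the call window |
| 14 days | edema, pruritus, peeling | always between call and visit |
| 21 days | bruising, tenderness/soreness, reduced range of motion | always between call and visit |
| 28 days | welting | within the day 23-37 window |
| 35 days | twitching, tingling, paresthesia, numbness | within the day 23-37 window |
| 56 days | burn, scarring, pigment change | between day 37 and day 83 after treatment #2 |
| 84 days | induration | within the day 83-97 window |

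Six limits (3 at 14 days, 3 at 21 days) lie between call and visit whichever days within the windows are used. After treatment #1 the 56-day limit is different: the 30-day follow-up visit comes 23 + 23 = 46 to 37 + 37 = 74 days after the first treatment, a range that includes day 56.

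**Delay in recall.** At a visit on day 23 to 37, the question whether an effect passed 14 days concerns a date 23 − 14 = 9 to 37 − 14 = 23 days earlier. For 21 days it is 23 − 21 = 2 to 37 − 21 = 16 days earlier.

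**Illustration for soreness.** From the pilot: mean 12.9 days, range 4-31, in 83% of 12 active subjects, which is 10. The lognormal shape is an assumption. The expected range of 10 normal values is 3.08 SD, so:

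- SD of log duration = ln(31/4)/3.08 = 0.665
- mean of log duration = ln(12.9) − 0.665²/2 = 2.336
- P(duration > 21 days) = 1 − Φ((ln 21 − 2.336)/0.665) = 0.143
- P(end between day 9 and day 23) = about 0.47

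With 20 treated subjects, 0.83 × 20 = 16.6 would have soreness, and 16.6 × 0.143 = 2.4 would truly exceed 21 days. The documents give no recall error. Simulating a normal error with assumed SDs gives, per treatment:

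| Assumed recall SD | True >21 days, missed | Wrongly called >21 days | Net change in count |
|---|---|---|---|
| 3 days | 11% (0.26 subjects) | 0.42 subjects | +0.16 |
| 5 days | 16% (0.38) | 0.84 | +0.45 |
| 7 days | 20% (0.48) | 1.38 | +0.90 |

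**The case against.** A reader might infer that most of the limits, 8 of 12, fall where nobody observes the subject. The documents do not support that. Reaching eight needs the 2-hour limit for acute pain and the 56-day limit. The first separates little, because mild or moderate pain beyond 2 hours can still be expected under the 3-week tenderness/pain row. The second lies outside the interval up to day 23-37 and is always in a gap only after treatment #2. Six limits, half of the table, is the secure count between call and visit.

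Nor is the subject unobserved in any general sense. AE forms are completed at the call and the visits, the skin is examined at visits, and section 11.3 has significant unscheduled contacts documented. A continuous effect still present at the day 23-37 visit has plainly passed any 2- or 3-week limit. Only effects that end between call and visit are ambiguous.

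A reader might also infer that dropping the pilot's day-14 contact created the problem for soreness. Section 1.6.5 says "Efficacy at 7, 14, 30, 37, 44, 60, 90, and 120 days was measured", with adverse events collected at every follow-up point. The pilot's own interval from day 14 to day 30 already contained day 21. Losing the contact about 14 days after each treatment therefore affects the 2-week limits, not the 3-week one. The pilot also reported durations in days, with no diary mentioned, so retrospective collection can yield durations, although their accuracy is unknown.

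Three further points stand. Figure 7.1.1 and the AE form are not available, so it cannot be ruled out that start and stop dates are already requested. Severe events are Adverse Events whatever their length, and serious events have their own reporting route. The safety output is a descriptive count, with no test or numerical threshold attached. These limit the consequences, but they do not supply an observed end date for an effect that stops between call and visit.

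**Conclusion.** The concern holds for the six 2- and 3-week limits after each treatment, and for the 8-week limit after treatment #2. That part follows from the visit windows alone and needs no modelling. What can be misclassified is a mild or moderate, typical effect; the means is recall of its end date; and the result is an entry in, or an omission from, the adverse event table.

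The effect is modest. On the assumed lognormal durations and recall SDs of 3 to 7 days, 0.3 to 0.5 subjects with soreness beyond 3 weeks are missed and 0.4 to 1.4 are wrongly added per treatment, a net shift of up to about one subject. Against about 2.4 true cases this is noticeable, but it does not support calling the adverse event results unreliable as a whole. The pilot durations may also not carry over, since this study delivers at least 720 lines per axilla at each treatment against a pilot total of 480. This is a cheap improvement worth making, not an invalid analysis.

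**What to change.** After each treatment, give the subject a one-page checklist of the Table 8.1.1 effects with a start day and a stop day for each, to be kept until every effect has stopped. Review it at the existing day 7 call and at the later visits. Add one sentence to section 7.1 saying that these dates are used for the duration test.

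The cost is one form and one protocol sentence. No visit, procedure or clinical rule changes. The drawbacks are a small burden on subjects and more mild events recorded than open questioning would produce.
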